1.0 Objectives*

1.1 The purpose of this study is to determine if an isometric gluteal activation home exercise program (HEP) combined with a movement retraining program utilizing feedback cues produces significant changes in scores on the Forward Step-Down Test (FSDT) in healthy young adults with movement coordination impairments.

- SA1: To determine if an isometric gluteal activation HEP with a movement retraining program with feedback cues produces significant changes on scores FSDT compared to the gluteal activation HEP alone.
- SA2: To determine if an isometric gluteal activation HEP followed with a movement retraining program with feedback cues produces significant changes on category FSDT compared to gluteal activation HEP alone.
- SA3: To determine if an isometric gluteal activation HEP with a movement retraining program with feedback cues produces changes in the peak activation of the gluteus medius and gluteus max during the FSDT compared to the gluteal activation HEP alone.
- SA4: To determine if an isometric gluteal activation HEP with a movement retraining program with feedback cues produces changes in the mean activation of the glute med and glute max during the FSDT compared to the gluteal activation HEP alone.
- SA5: To determine if HEP dose has an effect on the FSDT response, as measured by change in score on the FSDT.

1.2

- SA1: FSDT
 - H_0 : An HEP focusing on isometric gluteal activation with a movement retraining program with feedback cues will have no change on FSDT score.
 - H_1 : An HEP focusing on isometric gluteal activation with a movement retraining program with feedback cues will change FSDT scores more than a gluteal activation program alone.
- SA2: FSDT
 - H_0 : An HEP focusing on isometric gluteal activation with a movement retraining program with feedback cues will have no change on movement quality categorization.
 - H_1 : An HEP focusing on isometric gluteal activation with a movement retraining program with feedback cues will have a greater change on movement quality category than the gluteal activation program alone.

- SA3: Peak Activation, FSDT
 - H_0 : An HEP focusing on isometric gluteal activation with a movement retraining program with feedback cues will not produce a significant change MVIC of the glute med and glute max.

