9.5 N/A

10.0 Data and Specimen Banking

10.1 N/A

10.2 N/A

10.3 N/A

11.0 Data Management and Confidentiality

11.1 Data analysis plan and statistical procedures.

FSDT

Data processing: Each participant will perform a pre- and post- intervention trial for the FSDT that will be scored. The FSDT consists of 5 repetitions of a step-down task. One score is given for the whole test. One raters will score the FSDT (MM).

Data analysis: For the FSDT data, a 2x2 repeated measures ANOVA will be performed with significance set at alpha = .05. Post hoc testing will be used if significant differences are detected with the ANOVA. Tukey's HSD test will be used as the post hoc test, with significance set at alpha = .05.

sEMG

Data processing: Raw sEMG signals will be bandpass filtered between 10-500 Hz. The signal will be rectified, then smoothed using the Root Mean Square method with a 50ms window. The signal from the FSDT and UPST will be normalized to the MVIC obtained during the MVIC testing.

Data analysis: Following MVIC normalization, sEMG activity will be recorded during each of the outcome measures. Each FSDT step-down repetition will be analyzed as a separate trial, and the mean and peak activation for GMax and GMed will be extracted from each of the 5 trials. A mean value for each variable (mean and peak activation of GMax, mean and peak activation of GMed) will be calculated and recorded at the pre-and post-test sessions.

For the sEMG data, a 2x2 repeated measures ANOVA will be performed for each measurement (mean, peak) for each muscle (Gmed, Gmax), with significance set at alpha = .05. Post hoc testing will be used if significant differences are detected with the ANOVA. Tukey's HSD test will be used as the post hoc test, with significance set at alpha = .05.

11.2 G* power (Heinrich-Heine-University Dusseldorf, Dusseldorf, Germany) software was used to perform a priori power analysis to determine the

required N for this investigation. Data from [name] Et Al. (2025) study reported a Cohen's d of 0.58 (d=0.58).⁵ An N of 26 was calculated to achieve significant results with beta= .80 and alpha =.05 for a two-tailed hypothesis from an interaction effect of the 2x2 repeated measures ANOVA. Assuming 20% attrition, plus an additional 10% for FSDT screening failures, a final N=38 is required for this study.

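### Tukey's HSD after a 2x2 arm-by-time ANOVA is unnecessary, can be opened by any significant effect, and contains no comparison equal to the between-arm difference in change

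*Combined protocol and SAP*

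**What the plan says.** Section 11.1 gives the same two-stage rule twice. For the primary measure: "For the FSDT data, a 2x2 repeated measures ANOVA will be performed with significance set at alpha = .05". For the EMG outcomes, "a 2x2 repeated measures ANOVA will be performed for each measurement (mean, peak) for each muscle (Gmed, Gmax), with significance set at alpha = .05". That makes five ANOVAs. Each is followed by the same sentences: "Post hoc testing will be used if significant differences are detected with the ANOVA" and "Tukey's HSD test will be used as the post hoc test, with significance set at alpha = .05".

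Section 11.1 does not say which ANOVA effect opens the second stage, which means Tukey compares, or which error term it uses.

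Two other places show what the trial is meant to test. The SA1 alternative in section 1.2 is that the combined programme "will change FSDT scores more than a gluteal activation program alone"; SA3 and SA4 are also framed against the control programme. Section 11.2 derives the sample size "for a two-tailed hypothesis from an interaction effect of the 2x2 repeated measures ANOVA".

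**The concern.** Post hoc tests serve to find where a difference lies when a factor has three or more levels. Here arm has two levels, time has two levels, and their interaction is a single contrast. Tukey's HSD can add only pairwise comparisons of the four cell means, and those comparisons answer other questions than SA1, SA3 and SA4.

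The trigger is also wide. A time effect common to both arms is enough to open it. That is a plausible outcome with an active control: section 2.3 says the isometric programme alone has raised FSDT performance, though not to a clinically significant degree (section 2.1 is more guarded). The reader would then see separate pre-post tests for each arm and could take a significant result in one arm only as evidence that retraining works. The wording of section 1.2 makes this easier, because the SA1 null is that the combined programme produces no change, with no reference to the control, while the alternative is a between-arm statement.

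Finally, the six pairs mix comparisons within people and between people. One common error term cannot suit both.

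**Working it through.** **Inputs.** From section 11.2: d = 0.58, power 0.80, alpha .05, N = 26 before inflation, 20% attrition plus 10% screening failure, final N = 38. From section 9.2: equal allocation within strata, so 13 per arm at N = 26. Assumed, because the documents do not give them: pre-post correlation r (0.5, with a range), normal data, and the size of a change shared by both arms.

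**1. The plan's own figure.** With f = d/2 = 0.29 and two measurements, the interaction F test has noncentrality f² × N × 2/(1 − r) = 0.0841 × 26 × 2/0.5 = 8.75 on (1, 24) df. Power is 81.0%, so N = 26 is reproduced at r = 0.5. Inflation: 26/(1 − 0.30) = 37.1, rounded up to 38. The interaction is therefore the powered effect.

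**2. What Tukey could compare.** With cells ordered control pre, control post, experimental pre, experimental post, the difference in change has coefficients (1, −1, −1, 1). The six pairs are two pre-post pairs, two arm-versus-arm pairs and two diagonal pairs. Each has only two non-zero coefficients, so none is the target contrast.

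**3. How often the second stage opens.** Let both arms truly change by 0.58 SD of change. The time test then has noncentrality 26 × 0.58² = 8.75 and power 81%, while the arm and interaction tests each reject in 5%.
- Some effect significant: about 1 − 0.19 × 0.95 × 0.95 = 82.9%. Simulation gives 82.5%.
- Opened with a non-significant interaction: about 0.95 × (1 − 0.19 × 0.95) = 77.9%. Simulation gives 77.6%.

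The small gaps arise because the time and interaction tests share an error term. With an equal change of 0.8 SD (r = 0.5) the figures are 97.8% and 92.7%. With no effect at all, the stage opens in 13.7% (1 − 0.95³ = 14.3%).

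**4. Standard errors.** With score SD σ and n per arm, the true SE of a pre-post difference in means is σ√(2(1 − r)/n), and of an arm-versus-arm difference at one time σ√(2/n).
- Pooled between-cell error uses σ√(2/n) throughout. The pre-post SE is too large by 1/√(1 − r): 1.20, 1.41 and 1.83 at r = 0.3, 0.5 and 0.7.
- Within-subject error uses σ√(2(1 − r)/n) throughout. The arm-versus-arm SE is too small by √(1 − r): 0.84, 0.71 and 0.55 at the same r. Taken by itself, the post-test arm comparison then has a false-positive rate of about 6% at r = 0.5 and 14% at r = 0.7, against about 1% with pooled error.

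**5. The misleading pattern.** Equal true change of 0.58 SD of change, 13 per arm, Tukey run only when the ANOVA opens it:

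| Error term | Change found in experimental arm only |
|---|---|
| Within-subject, r = 0.3 to 0.8 | 18 to 19% |
| Pooled, r = 0.3 | 12% |
| Pooled, r = 0.5 | 6% |
| Pooled, r = 0.7 | 1% |

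The reverse pattern (control arm only) is about as frequent. The interaction test rejects in 5% of these trials, in either direction. With pooled error the rate also depends on the shared change: at r = 0.5 and 0.8 SD it is 16%.

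**The case against.** The strongest reply is that the right test is already in the plan. In a two-arm pre-post ANOVA the interaction is the between-arm difference in change, identical to a two-sample t test on change scores. A reader might infer that the trial never tests its main hypothesis, or that its sample size is undermined. Neither follows: the interaction is tested, and 11.2 powers it.

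A reader might also infer that the plan will declare a benefit when only the experimental arm shows a significant change. Nothing in 11.1 says that within-arm patterns decide SA1, SA3 or SA4. The risk lies in how extra results are read and reported.

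Nor do the documents support a flat statement that Tukey will treat correlated means as independent. The error term is unstated, and Tukey-adjusted comparisons with model-based repeated-measures standard errors would respect the pairing. What stands is that the classical test, as named, has one error term.

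Finally, it is tempting to add a second harm, failure to confirm a real effect. At a true 1.15 SD difference in change, the post-test arm pair agrees with a significant interaction in 68% (r = 0.5) or 41% (r = 0.7) of trials with pooled error, but in 89% or 83% with within-subject error. The two harms at their larger sizes belong to different error terms and cannot be added together. No text lets a non-significant pair override the interaction.

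**Conclusion.** The point holds as a should-fix. For all five ANOVA outcomes, the plan states a rule that is not needed, that a shared time effect can open, and that yields no comparison matching SA1, SA3 or SA4. Section 11.1 does not say that the interaction decides.

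The frequency of opening depends only on the shared change in SD-of-change units, not on r. The frequency of the one-arm pattern depends on the unstated error term and, with pooled error, heavily on r and on the size of the shared change. All simulated figures assume normal data and 13 per arm. The FSDT is a 0 to 6 score with entry restricted to 2 or more, so they indicate scale rather than exact rates.

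**What to change.** In both data-analysis paragraphs of section 11.1:

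1. Delete Tukey's HSD and the sentence that triggers it.
2. State that the arm-by-time interaction, reported as the between-arm difference in pre-to-post change with its estimate, 95% CI and p-value, is the only test of SA1, SA3 and SA4 for each outcome.
3. Report within-arm changes as supporting estimates with paired standard errors and 95% CIs, and state that significance in one arm but not the other is not evidence of a difference between arms.

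This changes wording only and removes tests; N = 38 stays. The cost is that the report can make no formal within-arm significance claims. The change should be made before the data are analysed.

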12.0 Provisions to Monitor the Data to Ensure the Safety of Subjects*

12.1 N/A

13.0 Withdrawal of Subjects

- 13.1 Non-study injuries that affect the ability to complete HEP or FSDT post-intervention will be withdrawn from the research without their consent.
- 13.2 If a participant no longer meets the inclusion or exclusion criteria or if the subject notifies the investigator that they no longer wish to continue participation in the study, the investigators will notify the participant that they have withdrawn from the study and will document the date and reason for withdrawal. The participant will return the compliance sheet to the investigators.

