3.0 Inclusion and Exclusion Criteria*

- 3.1 Individual eligibility will be determined through the Physical Activity Readiness Questionnaire Plus (PAR-Q+), which is a self-reported health questionnaire. During a presentation of inclusion/exclusion criteria, informed consent will be obtained as well. A preliminary FDST will be performed following informed consent to determine if the potential participant is eligible to participate in the study and for group stratification purposes.
- 3.2 Inclusion: Participants must be between the ages of 18 and older, if they were healthy via the PAR-Q+, and scored a 2 or higher on the FSDT.

Exclusion: Participants have any current knee/hip pain, past knee/hip pathology in the past 3 months on their dominant leg or that the participant believes would impact their ability to participate in the study, or any past LE surgery in their dominant leg that the participant believes would impact their ability to participate in the study, a concussion in the past 3 months, or if they have any vestibular pathology.

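### Sections 13.1–13.2 withdraw randomised participants for later events and seek no week-8 outcome, so the planned pre/post comparison becomes completers-only in effect and can be biased if loss differs by arm

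*Combined protocol and SAP*

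**What the plan says.** Section 9.2 places allocation after baseline EMG and FSDT testing. The home exercise program (HEP) then runs for eight weeks. Two rules in section 13.0 act during that period.

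- 13.1: "Non-study injuries that affect the ability to complete HEP or FSDT post-intervention will be withdrawn from the research without their consent". The two conditions are joined by *or*, so being unable to complete the HEP is enough, even if the participant could still do the week-8 FSDT.
- 13.2: withdrawal also follows "If a participant no longer meets the inclusion or exclusion criteria", or when the participant asks to leave. The exclusions in 3.2 begin with "Participants have any current knee/hip pain", a state that can arise during an exercise program.

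On withdrawal, 13.2 asks for the date, the reason and the compliance sheet. It does not ask for a final FSDT or sEMG.

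The analysis in 11.1 reads: "For the FSDT data, a 2x2 repeated measures ANOVA will be performed with significance set at alpha = .05". The sEMG variables get the same model. No analysis population, intention-to-treat statement, missing-data method or sensitivity analysis appears in the documents. Section 11.2 expects loss and inflates for it: "Assuming 20% attrition, plus an additional 10% for FSDT screening failures, a final N=38 is required for this study".

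**The concern.** Randomisation protects the comparison only if the people analysed are the people randomised, or if those lost are lost for reasons that act alike in both arms. Here a written rule removes participants for post-randomisation events and collects no outcome from them. A repeated measures ANOVA in its standard form cannot use a participant without a week-8 value. Section 11.1 does not mention completers; that is an inference, but these provisions lead straight to it.

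The arms could differ in such loss because only the experimental arm adds the single-leg Romanian deadlift, single-leg squat and split squat. Section 14.1 accepts that any exercise program carries an injury risk. The plausible arm-related route is new knee/hip pain under 13.2, or a participant choosing to stop. If those participants would also have shown poor FSDT change, the remaining experimental group looks better than the group that was randomised. SA1–SA4 all rest on this comparison.

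**Working it through.** **1. The plan's own figures.** Section 11.2 gives d = 0.58, and states: "An N of 26 was calculated to achieve significant results with beta= .80 and alpha =.05 for a two-tailed hypothesis" (beta there is evidently power). Take f = d/2 = 0.29, two groups, two time points, and a pre/post correlation of 0.5, which the plan does not state:

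- λ = f² × N × 2/(1 − 0.5) = 0.0841 × 26 × 4 = 8.75, with 1 and 24 df. Power is 0.810; N = 24 gives 0.775. So N = 26 is reproduced.
- Inflation: 26/(1 − 0.30) = 37.1, so 38. Taken in sequence, 26/0.8 gives 33 and 33/0.9 gives 37.

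**2. The yardstick.** The 2x2 interaction is a two-sample t-test on change scores. For equal arms λ = N × δ²/4, so δ = √(4 × 8.75/26) = 1.16 change-score SD. Solving for exactly 80% power at 13 per arm gives 1.15. An effect of 0.58 change-score SD would have power of only 0.29. Bias in change-score SD must therefore be set against about 1.15, not 0.58.

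**3. Assumed inputs.** The documents give no withdrawal rate by arm and no outcome for those withdrawn. Assume 38 × 0.9 = 34 randomised, 17 per arm, average loss of 20%, no true effect, and normal change scores. Let r be the correlation between the tendency to be withdrawn and poor change, from 0.3 to 0.7.

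**4. Bias.** If a fraction q of an arm is lost, the completers' mean is too favourable by r × k(q), where k(q) = φ(z)/(1 − q), z is the upper-q normal quantile and φ is the normal density. The bias in the difference is r × [k(q_exp) − k(q_ctl)].

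- k(0.10) = 0.195, k(0.15) = 0.274, k(0.20) = 0.350, k(0.25) = 0.424, k(0.30) = 0.497.

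| Loss, experimental v control | Bias in SD at r = 0.3 / 0.5 / 0.7 | Type I error (simulated) |
|---|---|---|
| 20% v 20% | 0 / 0 / 0 | 5% |
| 25% v 15% | 0.05 / 0.07 / 0.10 | 5.0% / 5.4% / 5.9% |
| 30% v 10% | 0.09 / 0.15 / 0.21 | 5.6% / 6.8% / 8.7% |

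Simulation error moves these slightly; other runs gave up to 0.11 SD and 6.4% in the second row, and up to 9.3% in the third.

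**5. A second model.** If those lost would have done D SD worse than completers in both arms, bias = (q_exp − q_ctl) × D. At 30% v 10% and D = 0.5 to 1.0 this is 0.20 × 0.5 = 0.10 to 0.20 × 1.0 = 0.20 SD, in agreement with step 4. Equal counts do not guarantee safety: with 20% lost in each arm but outcome-related loss only in the experimental arm, bias is again 0.20 × D = 0.10 to 0.20 SD.

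**6. Would a mixed model repair it?** Not by itself. With one baseline and one later score, it assumes that loss depends only on observed data. With a baseline-adjusted estimate (correlation 0.5) at 30% v 10%, bias falls only from 0.15 to 0.11 SD (r = 0.5) and from 0.21 to 0.16 SD (r = 0.7).

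**The case against.** The strongest reply is that 13.1 is confined to non-study injuries, so on its face it leaves out harm caused by the exercises. That stands. 13.1 still discards obtainable outcomes, but it is not evidence of loss tied to the arm unless injuries are mislabelled. The arm-related argument rests on 13.2 and voluntary stopping.

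The 13.2 route is also less automatic than it sounds. The table of events in 9.3 lists no pain assessment and no eligibility re-check, and the only visit between baseline and post-test is the week-4 form check. New pain would come to light mainly if a participant reported it. This too stands, and it limits how often the rule would act.

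Two stronger readings are tempting and should not be made:

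- *Improvers would be removed.* Taken literally, a score falling below 2 breaks an inclusion criterion. But the three FSDTs in 9.3 fit screening, baseline and post-test, so such a score can first appear once the outcome is in hand. Removing improvers would defeat SA2 and would work against the experimental arm.
- *The experimental arm carries more load.* The documents do not say so. Both arms receive the same resistance bands, and no external load is given for the three added standing exercises. The documented difference is the extra exercises.

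Finally, every loss rate and correlation above is assumed. That is correct, and equal loss with the same outcome relation gives no bias.

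**Conclusion.** The point holds as a weakness in the plan, not as a demonstrated bias. The withdrawal rules are explicit, the lack of any week-8 measurement after withdrawal is explicit in effect, and the completers-only comparison follows from these together with the silence of 11.1.

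Under moderate assumed imbalance the distortion is modest: about 0.05–0.11 change-score SD at 25% v 15% loss and 0.09–0.21 SD at 30% v 10%. The upper end, 0.21/1.15, is about 18% of the effect that the sample size can detect, with type I error near 9% instead of 5%. A reader might infer that the design favours the experimental arm; the documents give no loss by arm and no outcome for those withdrawn, so neither direction nor size can be asserted. It is worth correcting before follow-up begins, because a week-8 outcome that was never collected cannot be recovered.

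**What to change.** 1. In 13.1–13.2, state that eligibility is judged at entry for the purpose of remaining in the study and in the analysis. Separate stopping the HEP from leaving the study, so that anyone who stops the HEP is still invited to the scheduled week-8 FSDT/sEMG visit if willing and able. This is the main repair. Whether a participant stops exercising is left as it is.
2. In 11.1, analyse all randomised participants with outcome data in their assigned arm.
3. Report withdrawals by arm and reason, with one sensitivity analysis that assumes no FSDT change for those without a week-8 score. A mixed model may be used, but it is not the remedy for outcome-dependent loss.

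Cost: protocol wording, a few week-8 visits for non-completers, and a slightly diluted effect estimate. The required N does not change. On the plan's inputs with the assumed correlation of 0.5, power is 0.825 with 27 completers (38 × 0.9 × 0.8 = 27.4). It would be 0.906 if all 34 were measured, an upper limit before any dilution.

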13.3 N/A

14.0 Risks to Subjects

- 14.1 As with any exercise program, muscle soreness is a potential side effect. To reduce these potential side effects, participants will be asked to make sure that they put two days in between completing the HEP. Another risk with any exercise program is the potential risk of injury. To reduce these potential side effects participants will meet with investigators to be instructed on how to perform the exercises safely and will be cued during the HEP on proper form to complete the exercises .

14.2 N/A

14.3 N/A

14.4 N/A

15.0 Potential Benefits to Subjects

- 15.1 Potential benefits that individual subjects may experience from taking part in this research include improved movement quality and coordination during functional tasks.

